13.2 Reporting of Adverse Events and Adverse Drug Reactions

13.2.1. Legislation for Pharmacovigilance

Applicable legal base Pharmacovigilance for the Russian Federation is following:

- Federal law №61 of 12 April 2010 “On the Circulation of Pharmaceuticals”
- Good Pharmacovigilance Practice of Eurasian Economic Union” (came into force May 06, 2017).
- Roszdravnadzor order #1071 “On Approval of the Pharmacovigilance Procedure” (came into force April 01, 2017).
- Order of the Ministry of health care and social development of 26 August 2010 N757n “On approval of the procedure for drug safety monitoring, reporting of side effects, serious adverse drug reactions, unexpected adverse drug reactions”
- RF Government statement of 30.06.2004 #323 «On approval of the Federal Service on Surveillance in Healthcare»
- RF Government statement of 15.10.2012 №1043 «On approval of the Federal State Supervision in medicine circulation»

Applicable legal base Pharmacovigilance for the Republic of Kazakhstan is following:

- The Code of Republic of Kazakhstan on people's health and the health system (with amendments and additions from 19.05.2015)
- Order of the Minister of Health of the Republic of Kazakhstan dated November 19, 2009 № 744 On approval of rules of clinical trials and (or) pharmacological tests of medicines, medical devices and medical equipment (with amendments from September 28, 2012)
 - Order No. 421 of the Health and Social Development Minister of the Republic of Kazakhstan as of 29 May 2015 On Approval of the Rules for Medicines Pharmacovigilance and Monitoring of Adverse Reactions of the Medicines, Medical devices and Medical Equipment Order #9 on amendments to the Order #735 of the Minister of Health of the Republic of Kazakhstan from 18 November, 2009 On approval of the rules for state registration, renewal and amendments into the registration dossier of the Medicines, Medical devices and Medical Equipment
 - Good Pharmacovigilance Practice of Eurasian Economic Union" (came into force May 06, 2017).

Applicable legal base Pharmacovigilance for the Republic of Belarus is following:

- Law of the Republic of Belarus № 161-3 "On Medicines" dated 20.07.2006, ed. №386-3 dated 29.06.2016
- Technical Code of Practice 564-2015(33050) "Good Pharmacovigilance Practice"
- Good Pharmacovigilance Practice of Eurasian Economic Union" (came into force May 06, 2017).

13.2.2. AE Reporting Form

All AEs and ADRs will be documented in the special page of the eCRF – “AE reporting form”. The following information will be documented for each event:

- event term,
- start and stop date/ ongoing,
- severity,
- Investigator's opinion of the causal relationship between the event and administration of IBD medication(s) (related or not related),
- IBD medication,
- action concerning medication,
- outcome of AE,
- seriousness.

13.2.3. Collection and reporting of AEs and ADRs

The following safety data should be reported by the investigator to the responsible CRO:

- adverse drug reactions on IBD treatments,
- adverse events on Entivyo® (vedolizimab) treatment,
- serious adverse events on IBD treatments (including Entivyo® (vedolizumab) treatment).

Start of AEs and ADRs collection: AEs/ADRs must be collected from the date after ICF signing. Routine collection of AEs/ADRs will continue until Final visit (Visit 3).

A physician must report all reportable AEs and ARDs on the special “AE reporting form” provided by the Sponsor. The physician should record only one AE per 1 “AE reporting form”. The physician has to record the diagnosis if available. If no diagnosis is available, the physician should record each sign and symptom as separate reports.

13.2.4. Collection and reporting of SAE and pregnancies

The investigator must report all reportable SAEs and pregnancies to the CRO.

If information is not available at the time of the first report becomes available at a later date or upon on the Sponsor's request, the investigator should complete an additional SAE form and provide it by one of mentioned above way **immediately within 24 hours** of receipt. In any case all SAEs should be followed up until resolution or permanent outcome of the event. The timelines and procedure for follow-up reports are the same as those for the initial report.

Start of SAEs collection: SAEs must be collected from the date after ICF signing. Routine collection of SAEs will continue until Final visit (Visit 3).

The CRO must report all SAEs and pregnancies which occur during patient's treatment by Entyvio to the Sponsor **immediately within 24 hours** of receipt. All other SAEs and pregnancies are included in the study data base without direct reporting to the study Sponsor.

13.2.5. Safety reporting to Investigators, IECs and Regulatory Authorities

All safety-related data on study patient collected in the study database will be summarised in the Interim Analysis Study Reports and in the Non-Interventional Study Report. All Entyvio SAEs and pregnancy cases will be reported by CRO directly to Takeda within 24 hours.

The Sponsor is responsible for reporting all Entyvio serious adverse drug reactions (SADRs) to the Federal Service on Surveillance in Healthcare not later than 15 calendar days from the day when relevant information becomes known to the Sponsor or CRO.

Periodic Safety Update Report (PSUR) contains drug safety information obtained from spontaneous reports, literature and in clinical trials for a certain reporting period. If the PSUR submission time terms and frequencies for particular drugs are not established by Roszdravnadzor, PSUR submission time terms and frequency shall be calculated from the first drug's worldwide registration date (International Birth Date) and are as follows:

- Every 6 months during first 2 years from International Birth Date;
- Annually during the following 2 years;

- Once in three years – thereafter.

Specialized safety reporting in the Republic Kazakhstan:

The Investigator informs the Authorized organization, Ethics Committee and the Sponsor/responsible CRO about all ADRs not later than 15 calendar days from the day when relevant information becomes known.

Periodic Safety Update Report (PSUR) contains drug safety information obtained from spontaneous reports, literature and in clinical trials for a certain reporting period.

The marketing authorization holder, within the marketing authorization validity period, shall provide the authorized organization with the Periodic Safety Report from the date of registration in the Republic of Kazakhstan in accordance with the following standard periodicity:

- once every six months within two years after registration;
- annually - within the next three years;
- then - every three years or after receiving a report from the central office (if applicable);
- in future - upon subsequent medicine re-registration - once in five years;
- immediately at the authorized organization's request.

14 Data Quality Control and Assurance

14.1. Quality Control

14.1.1. Training of investigators

Before study start at the sites, all investigators will be sufficiently trained on the background and objectives of the study, study procedures, safety reporting, ethical as well as regulatory obligations. Investigators will have the chance to discuss and develop a common understanding of the study protocol and the case report form. All outcome variables and covariates will be recorded in a standardized case report form.

14.1.2. Study Quality Oversight

The data quality will be assured by using the following methods of quality review:

- telephone interview,

- monitoring in the study sites (the monitoring will consist of two parts: on-site interview and verification of the compliance of the data presented in the eCRF with the data of the primary documentation - source data verification (SDV)).

Due to non-interventional study design source documents will be partly reviewed for verification of data recorded on the eCRF. Source documents are defined as original documents, data, and records. The investigator and institution guarantee access to source documents by the Sponsor or its designee (CRO) and by the RA, IEC or LEC/IRB.

All aspects of the study and its documentation can be patient to review by the Sponsor or responsible CRO, including but not limited to the Investigator's Site File, patient medical records, informed consent documentation and review of eCRF and associated source documents. It is important that the investigator and other study personnel are available during the monitoring visits and that sufficient time is devoted to the process. The investigator and institution guarantee access to source documents by the Sponsor or responsible CRO and by the RA, IEC or LEC/IRB.

Due to the non-interventional study design it can be able to conduct quality review only on subset of investigational sites and case report forms. Exact extent of quality reviews will be defined in the Clinical Monitoring Plan. The detailed description of the quality review will be presented in the Quality Control Plan, the Clinical Monitoring Plan, the Data Management Plan (DMP) and Statistical Analysis Plan.

The investigational sites where telephone interview or monitoring visit will take place will be determined randomly. Due to long overall duration of the study several waves of quality reviews will be performed.

14.1.3. Protocol Deviations

The investigator should not deviate from the protocol, except where necessary to eliminate an immediate hazard to study patients. In accordance with NIS definition all examinations and other data should be registered in the CRF only if they are done in routine practice.

Should other unexpected circumstances arise that will require deviation from protocol-specified procedures and data collections rules, the investigator should consult with the Sponsor, responsible CRO or designee (and IRB or IEC, as required) to determine the appropriate course of action. There will be no exemptions (a prospectively approved deviation) from the inclusion or exclusion criteria.

In the event of a significant deviation, the site should notify the sponsor or its designee (and IRB or EC, as required). Significant deviations include, but are not limited to, those that involve fraud or misconduct, or confound interpretation of primary study assessment.

14.1.4. Data checks and data queries

After completion of the entry process, computer logic checks will be run to identify items, such as inconsistent dates, missing data, and questionable values. Queries may be issued by the sponsor and responsible CRO and will be answered by investigators.

Corrections to eCRF are recorded in an audit trail that captures the initial information, changes, identification of the person making the correction, the date the correction was made, and the reason for change. Reasons for significant corrections should additionally be included.

14.1.5. Quality Assurance Audits

The Quality Assurance (QA) unit or out-sourced by the Sponsor agency or appointed Qualified person may audit the study to ensure that study procedures comply with the protocol and standard operating procedures, applicable legislation and that collected data is correct and complete.

14.2 Inspection by IEC or Competent Authority

Representatives from IEC or Competent Authority may in rare cases wish to inspect the study on site. Upon receiving notification of such inspection, the investigator must immediately contact to the Sponsor and must make the records available as requested. The Inspector must be reminded up front that consent to access to personal data has been obtained from the participants in this study.

14.3 Data Handling and Record Keeping

14.3.1. Data Management Plan

Data handling will be carried out according to a Data Management Plan and Data Validation Plan. Data Management Plan must be written and approved before the design of the study database is finalised. Responsible CRO will provide all the data management service including data transferring, data clarification and quality control of the process. The data management provider should approve all data formats before the data collection tools are made available to the sites.

14.3.2. Data privacy

The Sponsor and responsible CRO affirm and uphold the principle of the patient's right to protection against invasion of privacy. The personal data of the NIS participants will be kept and processed with observance of the provisions of the RF federal law No. 152 "On personal data". Throughout this study, a patient's source data will only be linked to the study database or documentation via a unique identification number (for details, please, see Sections 8.5, 8.6., 8.7., 8.9).

If the written informed consent of a patient is known not to be available in spite of it being required, data for this patient is not entered into or is deleted from the database.

If a patient is included in the study in spite of being treated off-label (not according to the local SmPC), data is kept in the database and analysed separately and as part of the overall analyses as described in the Statistical Analysis Plan.

The patients will be identified in the database only by patient identification code (for details, please, see the section 8.7)

14.3.3. Case Report Form (CRF)

Electronic CRF (eCRF) will be used in the study. Completed eCRFs are required for each patient who signs an ICF.

The study database will be set up and maintained by responsible CRO. The responsible CRO will supply investigators with access to eCRF. The CRO will make arrangements to train investigators in the use of the eCRF. Patient data will be entered directly into the database by authorized investigators. These forms are used to transmit the information collected in the performance of this study to the Sponsor and regulatory authorities. eCRFs must be completed in Russian.

After completion of the entry process, computer logic checks will be run to identify items, such as inconsistent dates, missing data, and questionable values. Queries may be issued by CRO, Takeda personnel (or designees) and will be answered by the site.

Corrections to eCRFs are recorded in an audit trail that captures the initial information, changes, identification of the person making the correction, the date the correction was made, and the reason for change. Reasons for significant corrections should additionally be included.

The investigators must review the eCRFs for completeness and accuracy and must e-sign the appropriate eCRFs as indicated. Furthermore, the investigator must retain full responsibility for the accuracy and authenticity of all data entered on the eCRFs.

eCRFs will be reviewed for completeness and acceptability at the study site during periodic visits by the sponsor or its designee. The Sponsor or its designee will be permitted to review the patient's medical and hospital records pertinent to the study to ensure accuracy of the eCRFs. The completed CRFs are the sole property of the sponsor and should not be made available in any form to third parties, except for authorized representatives of appropriate governmental health or regulatory authorities, without written permission of the sponsor.

14.3.4. Coding of AEs and concomitant medications

Adverse events, medical history and concurrent medical conditions are coded with MedDRA dictionary (Medical Dictionary for Regulatory Activities). Concomitant Medications are coded with Anatomical Therapeutic Chemical Dictionary (ATC) current version.

14.3.5. Record retention

The investigator agrees to keep the records stipulated in Section 12.3.3 and those documents that include (but are not limited to) the study-specific documents, the Patient Identification list, medical records, all original signed and dated informed consent forms to enable evaluations or audits from regulatory authorities, the sponsor or responsible CRO. The study records should be retained until an amount of time specified by applicable regulatory requirements or for a time specified in the Study agreement. The investigator should contact and receive written approval from the sponsor before disposing of any such documents.

15 Statistical Methods and Determination of Sample Size

A statistical analysis plan (SAP) will be prepared and finalized prior to the first interim analysis. This section describes the statistical analyses as foreseen at the time of planning the study. Any known deviations from the planned analyses, the reason for such deviations and all alternative / additional statistical analyses that may be performed as well as the final statistical analysis must be described in a revised Statistical Analysis Plan (SAP) before completion of data collection. All later deviations and / or alterations will be summarised in the Non-interventional Study Report.

15.1 Patient Population

Due to observational nature of this study patients will not be excluded from analysis based on their performance and/or data availability. All obtained data will be summarised after procedures of data cleaning and verification. All planned analyses (including descriptive analyses and study listings) will be performed for Full Analysis Set of data.

The following patient's populations will be included into statistical analysis:

- *All Patients Enrolled population:* All patients who signed informed consent to enter the study
- *Safety population:* Patients who have taken at least one dose of any IBD medicine after enrolling in the study (Baseline visit)

15.2 The study data and Statistical Analysis methods

This study is observational and epidemiological methods will be employed for data analyses. Descriptive analysis will be performed of all collected data except data collected only for the purpose of data cleaning, i.e. all data listed in section 12.

The primary and secondary outcomes of the study are presented in section 6.2.

15.2.1. Summary of study data

All continuous variables will be summarised using the following descriptive statistics: n (non-missing sample size), mean, standard deviation, median, 25 percentile, 75 percentile, maximum and minimum. The frequency and percentages (based on the non-missing sample size) of observed levels will be reported for all categorical measures. For variables marked “binary” exact (Clopper-Pearson) 95% confidence intervals will be calculated where appropriate. For categorical variables with more than 2 categories 95% confidence intervals will be calculated using Goodman’s method [33].

In general, all data will be listed, sorted by site and patient, and when appropriate by visit number within patient. All summary tables will be structured with a column for each treatment pattern in the pre-defined order and will be annotated with the total population size relevant to that table/treatment pattern, including any missing observations.”

Patient Disposition

Data regarding how many patients reached the various stages of the study, how many dropped out, discontinued the treatment and for what reasons (death, ADRs, treatment failure, withdrew consent, lost to follow-up) will be presented for each subgroup and for study in bulk. Standard CONSORT diagram describing study patient flow will be provided.

15.2.2. Statistical analysis methods

All data from patients enrolled in this study will be analyzed. Information on CD and UC patients will be presented separately. Also, analysis will be performed separately by therapy subgroups (patients receiving non-biological therapy and patients receiving biological therapy). Due to complexity of treatment regimen a manual review can be used to define treatment subgroup for each patient.

A descriptive analysis approach will be used to analyze the data and the study outcomes for the different study subgroups.

Descriptive statistics will include summary tables (n, mean, median, standard deviation, minimum and maximum, lower and upper quartile for continuous variables and n, frequency and percentage for categorical values). Proportion will be assessed together with 95% confidence interval, if applicable. Cross tabulations will be used to present study outcomes by the corresponding subgroups, when required. Time to event will be described with Kaplan-Meier estimates. Median time to event will be presented together with the lower and upper quartiles. Baseline and retrospective data will be used to describe the patient population and will be tabulated separately.

The number and percentage of patients who have reached remission while in the study will be presented. Selected outcomes will be reported separately for those who have reached remission and those who haven't.

15.2.3. Analysis of Safety Data

All safety data will be analysed on the safety population. Prior to analysis, adverse drug reactions will be coded using MedDRA.

Incidence and characteristic of adverse drug reactions will be described and presented in summary tables using absolute frequencies and percentages as well as 95% confidence intervals;

Evaluation of AEs, including the AEs, will consist of the determination of total number of AEs, total number of patients with AEs and the number of AEs requiring discontinuation of the study treatment. The incidence and severity of all AEs will be summarized by body system. Treatment discontinuation due to AEs will be tabulated.

AEs reported in the study as well as AEs reported directly to authorities and to Takeda International Drug Safety according to section 11.2 and not captured in the study database will be

extracted from the overall safety database and the study database and listed or tabulated in the final report in the standard way of presenting such data in a Periodic Safety Update Report (PSUR).

15.2.4. Potential study biases

The study limitations are those inherent to uncontrolled observational studies. Taking into account observational and uncontrolled nature of the study, fully evaluating of non-biological /biological treatment effectiveness will not be available. However, data regarding in real-life practice will be gathered and analyzed. The inclusion criteria are those that used when administering non-biological /biological treatment in practice and therefore, the same criteria as those that would have been used if we had performed a similar prospective study. This type of experimental design should prevent selection bias that could occur when patient enrollment is related to the development of the outcome. In prospective observational study like this attrition bias is possible, however, in case of early leaving study last data will be gathered and effectiveness will be estimated, these cases will not be excluded from effectiveness analysis.

Details of the statistical analyses will be presented in the Statistical Analysis Plan.

15.2.5. Data handling

Missing data and invalid data

Missing data will not be restored. No procedures for missing data pattern assessment and/or imputation are planned.

Multiplicity

Because of descriptive nature of the study no multiplicity correction is applicable.

15.3 Interim Analyses

One interim data analysis is planned in this study – in 2019. The final statistical analysis will be performed after the end of the study and database lock.

15.4 Determination of Sample Size

The primary objective of this study is to obtain the accurate and comprehensive information regarding the treatment regimens used in patients with moderate to severe UC and CD flare within routine clinical practice in Russia, Belarus and Kazakhstan. For this purpose, sample size should be large enough to contain essential number of patients with different therapy options.

One of the key secondary objectives is to assess the percentage of Ulcerative Colitis (UC) and Crohn's Disease (CD) patients with at least one episode of failure of non-biological therapy with immunosuppressive agents or biological therapy registered within 12 months from the beginning of moderate to severe IBD flare. Based on literature data, up to 20-40% of IBD patients

experience failure of TNF antagonist therapy initially, and in 10-20% of patients per year loss of response is observed.

Assuming the percent of patients receiving biological therapy in the study population is 40%, about 40% proportion of CD patients [5, 6] and that 40-50% of the patients on biological therapy will have at least one episode of treatment failure during 12 months, enrolment of 2000 patients totally will be sufficient to estimate the proportion of patients on biological therapy with treatment failure during the 12 months of observation with acceptable precision in both UC and CD subgroups ($\pm 5.8\%$ for the smaller subgroup of CD patients and the assumed failure rate of 50%). The table below shows 95% confidence intervals for the estimated proportions of 40%, 50% and different sample size values. For other, more prevalent subgroups (CD patients on non-biological therapy, UC patients on each type of therapy) the proposed sample size will also allow to estimate proportion of patients with treatment failure with same or higher precision.

The total number of patients to be enrolled	The number of CD patients on biotherapy*	The number of CD patients in the analysis assuming 10% drop-out	Assumed failure rate of biotherapy**	
			40%	50%
2000	320	288	34.3-45.7%	44.2-55.8%
2500	400	360	34.9-45.1%	44.8-55.2%
3000	480	432	35.4-44.6%	45.3-54.7%
3500	560	504	35.7-44.3%	45.6-54.4%
4000	640	576	36.0-44.0%	45.9-54.1%
4500	720	648	36.2-43.8%	46.2-53.8%
5000	800	720	36.4-43.6%	46.3-53.7%

* Assuming the percent of patients receiving biotherapy is 40% among the study population. The precision (95% CI) is shown for the smaller subgroup of CD patients (approximately 40%).

** 95% confidence intervals are shown.

16 Reports

A Non-Interventional Study Report based on the results obtained will be prepared and submitted to the Sponsor for distribution. The Final Non-Interventional Study Report should be available within one year (12 months) from the date of the last data point collection, and the participating sites should be informed about the results when the report is finalised. Final Non-interventional Study Report should be provided to the IEC/RA (if applicable).

17 Publications

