11.1 Inclusion Criteria

Every eligible patient at participating investigational sites must meet the following criteria:

Inclusion criteria:

1. Male and female patients 18 years or older by the time of enrolment
2. Confirmed diagnosis of Crohn's disease or ulcerative colitis for at least 2 years prior to enrolment in the study.
3. The presence of a moderate to severe IBD flare at the time of enrolment or in patient anamnesis within 2 years before enrollment treated with steroids or/ and immunosuppressive agents or/ and biologic therapy. IBD flare(s) must be confirmed in the source documentation.
4. Current treatment with steroids or/ and immunosuppressive agents or/ and 5-ASA or/ and biologic therapy
5. Written informed consent, signed before the participation in the study begins.

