#### 8.1.3 Assessment of secondary and exploratory endpoints

**Each original treatment combination** (defined as the treatment combination that was used by the patient at the very start of retrospective observation period, i.e. first recorded treatment combination in the study) will be tabulated by the below listed parameters using the generic table format below (see example tables: Table 10, Table 11, Table 12 and Table 6):

- Demographic data;
- Disease activity at Visits 1, 2, 3 (Mayo, Harvey-Bradshaw indices);
- Disease status assessed by investigator at Visits 1, 2, 3;
- Frequency (percentage) of clinical, endoscopic and histologic remission at Visits 1, 2, 3 and retrospective period of observation;
- Extent of lesion at Visits 1, 2, 3;
- Systemic (extraintestinal) manifestations at Visits 1, 2, 3;
- Total number, duration and severity of disease exacerbations by Visit 1, 2 and 3;
- Total number, type and duration of disease complications by Visit 1, 2 and 3;
- Laboratory and instrumental assessments at Visits 1, 2, 3;
- Percentage of patient with surgical treatment by Visits 1, 2, 3 grouped by:
  - Indication;
  - Surgery type;
  - Presence of complications.
- Number of surgeries by Visits 1, 2, 3;

Protocol ID	MACS-2017-102279	STATISTICAL ANALYSIS PLAN	Page 25 of 41	
IP	N/A		Date	30.12.2021
ID	MACS-2017-102279_SAP		Version	v1.2 final

- Percentage of patients with at least one episode of failure or biological or/and non-biological therapy (e.g., dose escalation of biologics, switching to another therapy, IBD-related surgery, medication augmentation) by Visits 1, 2 and 3;
- Separately for patients who achieved / not achieved T2T treatment goals (based on the clinical assessment of IBD) by Visits 1, 2 and 3:
  - Presence of therapeutic de-escalation;
  - Presence of therapeutic escalation;
  - Continuation of therapy without any changes.
- Healthcare resources utilization:
  - Hospitalizations due to complications;
  - IBD-related surgeries;
  - Percentage of patients that used healthcare resources;
- Only for biological therapy - percentage (by Visits 1, 2, 3) of patients with:
  - Positive test results for TB before the start of biological therapy;
  - Active TB before the start of biological therapy;
- Percentage of patients by Visits 1, 2, 3 with:
  - Reactivation of TB;
  - New occurrence of TB.

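### The 12-month failure percentage on biologics pools recent starters with long-standing users, and no planned failure analysis separates them by time on the current drug

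*Protocol*

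**What the plan says.** **Planning rates.** Protocol 15.4, repeated in SAP 8.2, says that up to 20-40% of patients "experience failure of TNF antagonist therapy initially, and in 10-20% of patients per year loss of response is observed". It then sets one rate for everyone on a biologic, namely that "40-50% of the patients on biological therapy will have at least one episode of treatment failure during 12 months", and shows no derivation. On that basis "enrolment of 2000 patients totally will be sufficient to estimate the proportion of patients on biological therapy with treatment failure", with ±5.8% for Crohn's disease (CD) at a 50% rate.

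**Clock.** The same section counts failure within 12 months of the flare in one place and over the 12 months of observation in another. It never counts from the start of the biologic.

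**Who enters.** Protocol 11.1, criterion 4, requires "Current treatment with steroids or/ and immunosuppressive agents or/ and 5-ASA or/ and biologic therapy". Criterion 3 requires a treated moderate to severe flare at enrolment or in the two years before. Neither limits the time since the biologic was started.

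**How failure is reported.** SAP 8.1.3 lists "Percentage of patients with at least one episode of failure or biological or/and non-biological therapy" by Visits 1, 2 and 3. The table is split by the first regimen recorded in the two-year retrospective period, and again by treatment pattern where the pattern is large enough.

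**Subgroups.** SAP 7.4 uses time from diagnosis to prescription, steroid courses, first-line drug, drug sequence, route, activity, surgery, response to immunosuppressants, age and body mass index. Time on the current biologic is not among them. The split into biologic-naïve and previously treated patients is specified for the safety outcomes only (Protocol 6.2, SAP 7.1).

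**The concern.** The protocol's own sentence separates an early failure risk, which a patient faces on starting the drug, from a later yearly loss of response. A patient who has been on the drug for two years has passed the first and carries only the second. A patient who started last month carries both. A single percentage over the two depends on how many of each were enrolled.

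That share could differ between UC and CD, between sites and between drugs. Protocol 5.1 calls vedolizumab new, and JAK inhibitors entered the SAP in July 2019, inside the enrolment period planned in Protocol 10.2. It is a reasonable inference, though not stated anywhere, that average time on drug differs by drug. SAP 4.2 adds an objective to describe clinical outcomes in subgroups, SAP 7.4 defines subgroups by first-line drug, and SAP 8.1.1 plans an exploratory search for associations between treatment patterns and outcomes. A difference in treatment stage could be read there as a difference between drugs.

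**Working it through.** **1. Reproduce the plan's figure.** Inputs from Protocol 15.4: 2000 patients, 40% on biologics, 40% with CD, 10% drop-out.

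- n = 2000 × 0.4 × 0.4 × 0.9 = 288.
- Half-width at 50%: 1.96 × √(0.5 × 0.5 / 288) = 5.8%, interval 44.2-55.8%.
- At 40%: 1.96 × √(0.4 × 0.6 / 288) = 5.7%, interval 34.3-45.7%.

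Both match the table, as do its other rows. The full interval at 50% is 2 × 5.8 = 11.6 points wide.

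**2. Twelve-month rates from the cited figures.** Let i be initial failure (0.20-0.40) and l yearly loss of response (0.10-0.20).

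- Established users: l, so 10-20%.
- Starters, with loss of response acting on those who did not fail initially: i + (1 − i)l. This runs from 0.20 + 0.80 × 0.10 = 28% to 0.40 + 0.60 × 0.20 = 52%. At mid-range, 0.30 + 0.70 × 0.15 = 40.5%.

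**3. Gap between the groups.** i + (1 − i)l − l = i(1 − l).

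- Smallest: 0.20 × 0.80 = 16 points.
- Mid-range: 0.30 × 0.85 = 25.5 points.
- Largest: 0.40 × 0.90 = 36 points.

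**4. Effect of case mix.** With starter share f, the pooled rate is l + f × i(1 − l). The documents do not give f; 10% to 50% is an assumed range.

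| Starter share | Pooled rate at mid-range |
|---|---|
| 10% | 0.15 + 0.10 × 0.255 = 17.6% |
| 30% | 0.15 + 0.30 × 0.255 = 22.7% |
| 50% | 0.15 + 0.50 × 0.255 = 27.8% |

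The shift from 10% to 50% is 0.4 × gap: 6.4 points at the smallest gap, 10.2 at mid-range, 14.4 at the largest.

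**5. Can a mixed group reach 40-50%?** The required share is f = (target − l) / gap. The lower figure of each pair comes from simply adding i and l for starters (gap = i), the higher from step 2.

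- Mid-range, target 40%: 83% to 98% starters. Target 50% cannot be reached.
- Top of both ranges, target 40%: 50% to 63%. Target 50%: 75% to 94%.
- Bottom of both ranges: even all starters give only 28-30%.

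**6. Does precision suffer?** No. At n = 288 the half-width is 3.5% at a 10% rate, 4.6% at 20%, 5.3% at 30% and 5.8% at 50%. The planned 50% is the worst case.

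**The case against.** **The cited rates do not measure this endpoint.** They concern non-response and loss of response to TNF antagonists. The study's failure endpoint is an open composite that also counts dose escalation, augmentation, switching and surgery (Protocol 4.2 and 6.2), over several drug classes. Criterion 3 also selects patients with a recent treated flare, so established users here may fail more often than 10-20% a year. This stands. The absolute levels in the working are illustrative, and the gap for the composite could differ from 16 to 36 points.

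**The SAP already separates the groups in part.** A patient on a biologic from the start of the retrospective window and one who moved onto it later have different first recorded regimens, and patterns are followed in six-month steps. This is true but indirect. Two patients who both began the window on an immunosuppressant, and changed to the same biologic 18 months and 1 month before Visit 1, share a first regimen. They part only at pattern level, where failure is tabulated only if the pattern is large enough.

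**The study is descriptive.** Protocol 15.2.4 concedes that effectiveness cannot be fully evaluated, and no comparison of failure between sites is planned. This limits the harm but does not remove it, because SAP 8.1.1 still looks for associations between patterns and outcomes.

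**A tempting stronger reading** is that the 40-50% planning rate fits new starters only. The documents do not support it: step 5 shows that mixed groups can reach it at the top of the cited ranges, the composite may run higher than the cited rates, and the protocol does not derive 40-50% from them.

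**Conclusion.** The point holds as one of interpretation. A key secondary percentage pools two groups that the protocol's own figures distinguish, and no planned failure analysis splits them directly. On those figures, a change in starter share from 10% to 50% moves the pooled rate by 6.4 to 14.4 points, about 10 at mid-range. This rests on TNF-antagonist rates standing in for the composite and on an assumed range of shares.

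The fair yardstick is the full interval of 11.6 points. A reader might set the shift against the ±5.8% half-width and call it about double; that compares an end-to-end range with half an interval. Like for like, the shift is of the same order as the sampling uncertainty: below the interval width at the small end and above it at the large end.

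A reader might also infer that the sample size is inadequate. It is not: the stated precision reproduces and is the worst case. The change is worth making because it is cheap. It is not a condition for the study's validity.

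**What to change.** In SAP 8.1.3, add a table of the 12-month failure percentage on biologics by time since start of the current biologic at Visit 1, for example up to 6 months versus longer. Give it separately for UC and CD, beside the pooled figure. Use the same split wherever failure is compared between drugs or treatment patterns. Patients who start a biologic only after Visit 1 have no time on drug at that visit and need a row of their own.

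In Protocol 15.4 and SAP 8.2, do not assign 40-50% to new starters. At most, note that it is an assumption for the mixed group and is not derived from the two cited rates.

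**Cost.** No new data are needed: Protocol 12.6.1 records the start date and the induction or supportive regimen for each biologic, and the two-year treatment history covers a 6-month cut. The cut-point is a choice and should be fixed before the failure results are seen. SAP v1.2 is dated 30.12.2021, so the addition would be documented as a later change under SAP 8.5 and Protocol 15. The price is wider intervals: if the 288 CD patients split evenly, each stratum of 144 has 1.96 × √(0.25 / 144) = ±8.2% at a 50% rate, against ±5.8% pooled.
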